5.1 Definition for Analysis Populations

RZB Population:

The RZB population consists of subjects who were randomized to risankizumab 150 mg in Studies 1311.3, 1311.30, 1311.28, 1311.38, and M16-178. This population will be used to evaluate the long-term safety and efficacy of risankizumab 150 mg with loading dose. For subjects from Japan, data after the first dose of risankizumab 150 mg from the preceding studies, and prior to the start of 75 mg dose will be used for the analyses.

RZB_NL Population:

The RZB_NL population consists of subjects who were randomized to placebo in the initial study and switched to risankizumab 150 mg (without loading dose) in Studies 1311.3, 1311.4, 1311.28, and 1311.38. This population will be used to evaluate the long-term safety and efficacy of risankizumab 150 mg without initial loading dose. For subjects from Japan, data after the first dose of risankizumab 150 mg from the preceding studies, and prior to the start of 75 mg dose will be used for the analyses.

Retreatment Population:

The Retreatment population consists of subjects who were re-randomized to placebo in Part B of Study 1311.4 and received retreatment of risankizumab 150 mg. This population will be used to evaluate the safety and efficacy of re-treatment after temporary withdrawal. For subjects from Japan, data after the re-treatment and prior to the start of 75 mg dose will be used for the analyses.

UST_RZB Population:

The UST_RZB population consists of subjects who were randomized to ustekinumab in Studies 1311.3 and 1311.28. This population will be used to assess the safety and efficacy of risankizumab 150 mg when subjects switch from ustekinumab to risankizumab

150 mg. For subjects from Japan, data prior to the start of 75 mg dose will be used for the analyses.

ADA RZB Population:

The ADA_RZB population consists of subjects who were randomized to adalimumab in Study 1311.30 and switched to risankizumab. This population will be used to assess the safety and efficacy of risankizumab when subjects from adalimumab to risankizumab.

FUM RZB Population:

The FUM_RZB Population consists of subjects who were randomized to Fumaderm[®] (fumaric acid esters) in Study M16-178. This population will be used to assess the safety and efficacy of risankizumab when subjects switch from Fumaderm[®] to risankizumab.

RZB Japan Population:

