For efficacy analyses, local tolerability, laboratory parameters, and vital sign variables, analysis windows are constructed using the following algorithm:

- Determine the nominal Rx day for each visit (e.g., Week 4 [4 weeks after Baseline visit] equals Rx Day 29).
- In order to include all post baseline data, the first post-baseline interval starts on the first day after the first dose of risankizumab (Rx Day 2).
- Determine the window around a specific nominal Rx day by adding or subtracting half of the interval between adjacent visits (e.g., days between Week 2 and Week 4 is 14). The threshold between adjacent visits is determined by splitting the interval evenly between the visits. If the resulting split is between Rx days, then the threshold is determined as the midpoint between the adjacent visits. If the resulting split is on an Rx day, then the threshold is determined as being between that Rx day and the Rx day prior to it (e.g., the split between Week 2 and Week 4 would be between Rx Days 22 and 23).
- If more than one assessment is included in a time window the assessment closest to the nominal day will be used. If there are two observations

equidistant to the nominal day, the one after the nominal day will be used in analyses. If more than one post baseline assessment is included on the same day, then the worst assessment on that day will be used in analyses, except those specified in Section 11.0.

The protocol specified visits and corresponding time windows used in the efficacy analyses, local tolerability, laboratory parameters, and vital sign variables, are presented in the following tables.

Table 1. Visit Windows for Analysis of PASI, sPGA, Local Tolerability Assessment, Clinical Laboratory Tests, and Vital Signs (RZB Population)

Window Label	Target Day	Interval
Baseline ^a	1	≤ 1 ^b
Week 4	29	[2, 43]
Week 8	57	[44, 71]
Week 12	85	[72, 99]
Week 16	113	[100, 155]
Week 28	197	[156, 239]
Week 40	281	[240, 323]
Week 52	365	[324, 407]
Week 64	449	[408, 491]
Week 76	533	[492, 575]
Week 88	617	[576, 659]
Week 100	701	[660, 743]
Week 112	785	[744, 827]
Week 124	869	[828, 911]
Week 136	953	[912, 995]
Week 148	1037	[996, 1079]
Week 160	1121	[1080, 1163]
Week 172	1205	[1164, 1247]
Week 184	1289	[1248, 1331]
Week 196	1373	[1332, 1415]
Week 208	1457	[1416, 1541]
Week 232	1625	[1542, 1709]
Week 256	1793	[1710, 1877]
Week 280	1961	[1878, 2045]
Week 304	2129	[2046, 2199]

a. There is no baseline for local tolerability measurements.

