b. If time is collected in vital signs, restrict to records prior to the first dose of study drug.

Note: Rx Day calculated relative to first dose date of risankizumab.

Table 2. Visit Windows for Analysis of Efficacy Variables (DLQI/NAPSI/PSSI/PPASI) (RZB Population)

Window Label	Target Day	Interval
Baseline	1	≤ 1
Week 16	113	[2, 239]
Week 52	365	[240, 449]
Week 76	533	[450, 617]
Week 100	701	[618, 785]
Week 124	869	[786, 953]
Week 148	1037	[954, 1121]
Week 172	1205	[1122, 1289]
Week 196	1373	[1290, 1415]
Week 208	1457	[1416, 1541]
Week 232	1625	[1542, 1709]
Week 256	1793	[1710, 1877]
Week 280	1961	[1878, 2045]
Week 304	2129	[2046, 2199]

Note: Rx Day calculated relative to first dose date of risankizumab.

Table 3. Visit Windows for Analysis of PASI, sPGA, Local Tolerability Assessment, Clinical Laboratory Tests, and Vital Signs (RZB_NL Population)

Window Label	Target Day	Interval
Switch to RZB	1	$\leq 1^a$
Week 12S	85	[2, 127]
Week 24S	169	[128, 211]
Week 36S	253	[212, 295]
Week 48S	337	[296, 379]
Week 60S	421	[380, 463]
Week 72S	505	[464, 547]
Week 84S	589	[548, 631]
Week 96S	673	[632, 715]
Week 108S	757	[716, 799]
Week 120S	841	[800, 883]
Week 132S	925	[884, 967]
Week 144S	1009	[968, 1051]
Week 156S	1093	[1052, 1135]
Week 168S	1177	[1136, 1219]
Week 180S	1261	[1220, 1303]
Week 192S	1345	[1304, 1429]
Week 216S	1513	[1430, 1597]
Week 240S	1681	[1598, 1765]
Week 264S	1849	[1766, 1933]
Week 288S	2017	[1934, 2087]

S = Switch to Risankizumab

a. If time is collected in vital signs, restrict to records prior to the first dose after switch to RZB.

Note: Rx Day calculated relative to first dose date of risankizumab for subjects switched from Placebo.

**Table 4. Visit Windows for Analysis of Efficacy Variables
 (DLQI/NAPSI/PSSI/PPASI) (RZB_NL Population)**

Window Label	Target Day	Interval
Switch to Risankizumab	1	≤ 1
Week 36S	253	[2, 337]
Week 60S	421	[338, 505]
Week 84S	589	[506, 673]
Week 108S	757	[674, 841]
Week 132S	925	[842, 1009]
Week 156S	1093	[1010, 1177]
Week 180S	1261	[1178, 1303]
Week 192S	1345	[1304, 1429]
Week 216S	1513	[1430, 1597]
Week 240S	1681	[1598, 1765]
Week 264S	1849	[1766, 1933]
Week 288S	2017	[1934, 2087]

S = Switch to Risankizumab

Note: Rx Day calculated relative to first dose date of risankizumab for subjects switched from Placebo.

Table 5. Visit Windows for PASI and sPGA (Relapsed and Retreatment Subjects in Retreatment Population)

Window Label	Target Day	Interval
Entry of Retreatment	1	≤ 1
Week 8R	57	[2, 85]

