Week 16R	113	[86, 155]
Week 28R	197	[156, 239]
Week 40R	281	[240, 323]
Week 52R	365	[324, 407]
Week 64R	449	[408, 491]
Week 76R	533	[492, 575]
Week 88R	617	[576, 659]
Week 100R	701	[660, 743]
Week 112R	785	[744, 827]
Week 124R	869	[828, 911]
Week 136R	953	[912, 995]
Week 148R	1037	[996, 1079]
Week 160R	1121	[1080, 1163]
Week 172R	1205	[1164, 1289]
Week 196R	1373	[1290, 1457]
Week 220R	1541	[1458, 1625]
Week 244R	1709	[1626, 1793]
Week 268R	1877	[1794, 1961]
Week 292R	2045	[1962, 2115]

R = Retreatment of Risankizumab

Note: Rx Day calculated relative to first dose date of retreatment with risankizumab.

Table 6. Visit Windows for PASI and sPGA (OLE Retreated Subjects in Retreatment Population)

Window Label	Target Day	Interval
Entry of OLE	1	≤ 1
Week 12R	85	[2, 127]
Week 24R	169	[128, 211]
Week 36R	253	[212, 295]
Week 48R	337	[296, 379]
Week 60R	421	[380, 463]
Week 72R	505	[464, 547]
Week 84R	589	[548, 631]
Week 96R	673	[632, 715]
Week 108R	757	[716, 799]
Week 120R	841	[800, 883]
Week 132R	925	[884, 967]
Week 144R	1009	[968, 1051]
Week 156R	1093	[1052, 1177]
Week 180R	1261	[1178, 1345]
Week 204R	1429	[1346, 1513]
Week 228R	1597	[1514, 1681]
Week 252R	1765	[1682, 1849]

R = Retreatment of Risankizumab

Note: Rx Day calculated relative to first dose date of retreatment with risankizumab.

Table 7. Visit Windows for DLQI, NAPSI, PSSI, and PPASI (OLE Retreated Subjects in Retreatment Population)

Window Label	Target Day	Interval
Entry of OLE	1	≤ 1
Week 24R	169	[2, 253]
Week 48R	337	[254, 421]
Week 72R	505	[422, 589]
Week 96R	673	[590, 757]
Week 120R	841	[758, 925]
Week 144R	1009	[926, 1093]
Week 156R	1093	[1094, 1177]
Week 180R	1261	[1178, 1345]
Week 204R	1429	[1346, 1513]
Week 228R	1597	[1514, 1681]
Week 252R	1765	[1682, 1849]

R = Retreatment of Risankizumab

Note: Rx Day calculated relative to first dose date of retreatment with risankizumab.

Table 8. Visit Windows for PASI, sPGA, Local Tolerability Assessment, Clinical Laboratory Tests, and Vital Signs (ADA_RZB Population)

Window Label	Target Day	Interval
Switch at Week 16		RxDay_B
Switch to Risankizumab	1	$\leq 1^a$
Week 4S	29	[2, 43]
Week 8S	57	[44, 71]
Week 12S	85	[72, 99]
Week 16S	113	[100, 127]
Week 20S	141	[128, 155]
Week 24S	169	[156, 183]
Week 28S	197	[184, 239]
Week 40S	281	[240, 323]
Week 52S	365	[324, 407]
Week 64S	449	[408, 491]
Week 76S	533	[492, 575]
Week 88S	617	[576, 659]
Week 100S	701	[660, 743]
Week 112S	785	[744, 827]
Week 124S	869	[828, 911]
Week 136S	953	[912, 995]

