10.0 Efficacy Analysis

10.1 General Considerations

The efficacy analysis will be performed for each population except the ALL_RZB Population. The efficacy analysis will use the data from this study and preceding study after subjects started to take risankizumab. The BL values (baseline values from the

preceding studies) will be used to determine responses and changes in the efficacy variables.

Continuous variables will be summarized by the number of observations, mean, standard deviation, median, minimum, maximum, 25th and 75th percentiles, as well as the 95% confidence intervals (CIs) of the mean values. Categorical variables will be summarized by counts and percentages, as well as the 95% CIs of the percentages. No statistical tests will be performed in this study.

Missing data will be imputed using the following methods for the efficacy analyses:

- Last Observation Carried Forward (LOCF): The LOCF analyses will use the last observed non-missing evaluation (last completed non-missing evaluation, from composite endpoint) from the previous visit within the particular period for efficacy measures assessed to impute missing data at later visits in the same period. Baseline efficacy evaluations will not be carried forward. Of note, post-baseline observations from Part A1 in Study 1311.4 can be carried forward to ITT_A2 subjects from ARM 1 since treatment is the same.
- As-Observed Cases (OC): The as-observed analysis will not impute values for missing evaluations, and thus a subject who does not have an evaluation on a scheduled visit will be excluded from the as-observed analysis for that visit.

LOCF will be used as the primary imputation method and OC will be used as sensitivity analysis for both categorical variables and continuous variables. Both LOCF and OC will not include values after discontinuation of study drug.

All endpoints will be analyzed up to the last visit with at least one subject has observed measurements of that variable, by the time of the interim data cutoff.

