10.3 Additional Efficacy Analyses

The following additional efficacy variables will be summarized at all visits for each population:

- Proportion of subjects achieving $\geq 50\%$ reduction in PASI score (PASI 50)
- Proportion of subjects achieving absolute PASI of < 3
- Proportion of subjects achieving DLQI score of 0
- Proportion of subjects achieving DLQI score of 0 or 1
- Proportion of subjects achieving a reduction of at least 5 points in DLQI, among subjects with baseline value ≥ 5
- Change and percent change from baseline in PASI
- Change and percent change from baseline in DLQI
- Change and percent change from baseline in NAPSI, among subjects with baseline value > 0
- Change and percent change from baseline in PPASI, among subjects with baseline value > 0
- Change and percent change from baseline in PSSI, among subjects with baseline value > 0

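### Relapsed-and-retreated subjects in the Retreatment Population have visit windows for PASI and sPGA only, although the SAP requires DLQI, NAPSI, PSSI and PPASI summaries for every efficacy population

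*SAP*

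**What the plan says.** SAP 5.1 defines one population: "The Retreatment population consists of subjects who were re-randomized to placebo in Part B of Study 1311.4 and received retreatment of risankizumab 150 mg". Its purpose is also given there: "This population will be used to evaluate the safety and efficacy of re-treatment after temporary withdrawal".

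SAP 6.0 ties the analysis to printed windows. It says that the visits and "corresponding time windows used in the efficacy analyses, local tolerability, laboratory parameters, and vital sign variables, are presented in the following tables". For the Retreatment Population there are three tables:

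- Table 5: "Visit Windows for PASI and sPGA (Relapsed and Retreatment Subjects in Retreatment Population"
- Table 6: "Visit Windows for PASI and sPGA (OLE Retreated Subjects in Retreatment Population"
- Table 7: "Visit Windows for DLQI, NAPSI, PSSI, and PPASI (OLE Retreated Subjects in Retreatment Population"

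The SAP's own list of tables carries the same three titles, so no table was lost in text extraction.

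On scope, SAP 10.1 states "The efficacy analysis will be performed for each population except the ALL_RZB Population". SAP 10.3, which contains the DLQI, NAPSI, PPASI and PSSI variables, opens with "The following additional efficacy variables will be summarized at all visits for each population". SAP 10.4 applies the same lists to the interim analysis. Protocol 5.3.3.2 promises summaries at every visit where the variable is evaluated.

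**The concern.** Visit-based summaries need a rule that places each assessment at a visit. For relapsed-and-retreated subjects that rule exists for PASI and sPGA and is absent for the other four instruments, yet the SAP asks for those instruments in the whole population.

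A programmer could leave the cohort out, borrow the Table 5 grid, borrow Table 7, or build a new grid. These choices give different tables, and the choice would be made with open-label data in hand. If the cohort is left out, the quality-of-life, nail, palmoplantar and scalp results labelled Retreatment would describe only subjects who restarted at OLE entry. The population is meant to describe re-treatment after withdrawal in both groups.

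**Working it through.** **1. Coverage of the window tables (SAP 6.0).**

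| Population or cohort | PASI, sPGA | DLQI, NAPSI, PSSI, PPASI |
|---|---|---|
| RZB | Table 1 | Table 2 |
| RZB_NL | Table 3 | Table 4 |
| Retreatment, relapsed and retreated | Table 5 | none |
| Retreatment, OLE retreated | Table 6 | Table 7 |
| ADA_RZB, switch at Week 16 | Table 8 | Table 9 |
| ADA_RZB, switch at OLE | Table 8 | Table 9 |
| UST_RZB, FUM_RZB, RZB_Japan | Table 10 | Table 11 |

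ADA_RZB is the closest comparison because it also has two start points. Both are covered for both sets of instruments.

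**2. Is the gap intended?** Where the SAP leaves Retreatment out of an analysis, it does so by listing the populations included. SAP 11.1 does this for laboratory and vital-sign change, shift tables and local tolerability. SAP 10.3 has no such list, and SAP 14.1 records no departure from the protocol.

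**3. What is affected.** Of the ten bullets in SAP 10.3, three rest on PASI (PASI 50, PASI below 3, change in PASI) and are served by Table 5. The other seven rest on DLQI, NAPSI, PPASI or PSSI. Appendix C schedules these instruments at OLE Weeks 0, 24, 48, 72, 96, 120, 144, 156, 180, 204, 228 and EOT, which is 12 assessments.

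**4. Can Table 7 be reused?** Rx Day is 7 × week + 1, counted from the first retreatment dose. For relapsed subjects that dose precedes OLE entry. The documents do not give the interval, so 16, 28 and 40 weeks are assumed here.

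- At 16 weeks the OLE assessments fall at 16R, 40R, 64R and so on; at 28 weeks at 28R, 52R, 76R; at 40 weeks at 40R, 64R, 88R. None of these series meets a Table 7 target week.
- At 16 weeks, OLE Week 24 is 40R, day 281. Table 7 would label it 48R, eight weeks late.
- At 16 weeks, EOT is 252 + 16 = 268R, day 1877, past the end of Table 7 at day 1849. At 28 and 40 weeks it falls on days 1961 and 2045, also past the end.

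**5. Reproducing Table 5.** Each boundary is the midpoint of adjacent targets: (57 + 113)/2 = 85, (113 + 197)/2 = 155, and so on to (1877 + 2045)/2 = 1961. All 19 internal boundaries match. The printed tables give the midpoint day to the earlier window, as does the SAP's Week 2/Week 4 example (midpoint 22, split between 22 and 23). That convention is kept below.

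**6. An example grid.** Table 5 changes from 12-week to 24-week steps at 172R, and Appendix C does so at Week 156. 172 − 156 = 16, so Table 5's layout is consistent with OLE entry at about 16R. On that assumption the 12 assessments fall at 16R, 40R, 64R, 88R, 112R, 136R, 160R, 172R, 196R, 220R, 244R and 268R. Table 5's 292R is kept as the last window. The midpoints are:

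- (113 + 281)/2 = 197
- (281 + 449)/2 = 365
- (449 + 617)/2 = 533
- (617 + 785)/2 = 701
- (785 + 953)/2 = 869
- (953 + 1121)/2 = 1037
- (1121 + 1205)/2 = 1163
- (1205 + 1373)/2 = 1289

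From 196R onward the boundaries are those of Table 5.

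**7. How far the example carries.** At 40 weeks every assessment still has its own window, but OLE Week 144 (184R, day 1289) takes the 172R label. At 28 weeks OLE Week 144 (172R, day 1205) and Week 156 (184R, day 1289) both fall in [1164, 1289], so one is discarded. Several others land on a window edge, such as day 197 in [2, 197]. The final targets therefore depend on the actual intervals.

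**The case against.** The strongest reply is that a missing table is not an exclusion. SAP 5.1 puts both cohorts in the population, SAP 10.3 asks for the variables in each population, and SAP 6.0 describes a general way to build windows. That is right as far as it goes. A reader might infer that the SAP restricts these results to OLE restarters, but no sentence says so. What stands is that the algorithm needs nominal visits, and none are listed for this cohort and these instruments.

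A reader might also infer that recovery after loss of response goes unreported. It does not. Table 5 covers PASI and sPGA from 8R to 292R, which supports all five key variables and three of the additional ones. Nor do the documents show that the four instruments were collected at relapse or early in retreatment within Study 1311.4. Only the OLE assessments are certain to be scheduled, so a new table may add mainly long-term status.

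It is also tempting to call the OLE-retreated group selected on outcome. That rests on table titles alone, because the relapse and retreatment rules of Study 1311.4 are not in these documents.

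Finally, the data are not wholly unused. Subjects from Japan are also in the RZB Japan Population, and Table 11 gives that population windows for these instruments in the OLE.

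**Conclusion.** The gap is real and conflicts with SAP 10.1 and 10.3. Within the Retreatment Population, DLQI, NAPSI, PSSI and PPASI have windows for one of two cohorts. Either the relapsed cohort drops out of these summaries or it is summarised on windows that are not pre-specified.

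Up to 12 scheduled OLE assessments per instrument and relapsed subject are affected. Twelve is a ceiling. Values after study drug discontinuation are excluded (SAP 10.1), data from Japan after the start of the 75 mg dose are not used in this population (SAP 5.1), and the change and percent-change summaries for NAPSI, PPASI and PSSI need a baseline above 0 (SAP 10.3). The number of relapsed subjects is not given.

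Severity is low to moderate: the outcomes are additional and descriptive, efficacy is the secondary objective, no tests are planned, and PASI and sPGA are untouched.

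**What to change.** Before database lock, do one of two things.

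1. **Add a DLQI, NAPSI, PSSI and PPASI window table for relapsed-and-retreated subjects.** Count Rx Day from the first retreatment dose. Take targets from the Appendix C schedule, including the 12-week step from Week 144 to Week 156, and from the actual retreatment-to-OLE intervals. Split at midpoints as the printed tables do. If OLE entry is at about 16R, this gives 16R [2, 197], 40R [198, 365], 64R [366, 533], 88R [534, 701], 112R [702, 869], 136R [870, 1037], 160R [1038, 1163], 172R [1164, 1289], 196R [1290, 1457], then as in Table 5 to 292R [1962, 2115]. Check this against the observed intervals before adopting it.
2. **State in SAP 10.3 that these endpoints are limited to OLE-retreated subjects, and why.**

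The first costs one SAP table and a rerun of existing programs, with no new data for the OLE visits. The second costs a sentence. If Table 7 serves as the template, correct its Week 144R/156R boundary first: it prints [926, 1093] and [1094, 1177], which leaves the 156R target day, 1093, outside its own window.

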Appendix C. Study Activities Flow Chart

Activity	Visit 1/Baseline ^a	Visit 2/Week 12	Visit 3/Week 24	Visit 4/Week 36	Visit 5/Week 48	Visit 6/Week 60	Visit 7/Week 72	Visit 8/Week 84	Visit 9/Week 96	Visit 10/Week 108	Visit 11/Week 120	Visit 12/Week 132	Visit 13/Week 144	Visit 14/Week 156	Week 168	Visit 15/Week 180	Week 192	Visit 16/Week 204	Week 216	Visit 17/Week 228	Week 240	EOT Visit ^b	EOO Visit
Informed Consent ^c	X																						
Inclusion/exclusion criteria	X																						
Demographics ^d	X																						
Medical/Surgical History ^e	X																						
Prior and Concomitant Therapy Assessment	X ^f	X	X	X	X	X	X	X	X	X	X	X	X	X		X		X		X		X	X
Adverse Event Assessment ^g	X ^f	X	X	X	X	X	X	X	X	X	X	X	X	X		X		X		X		X	X
Physical Exam ^h	X ^f	X	X	X	X	X	X	X	X	X	X	X	X	X		X		X		X		X	
Electrocardiogram (ECG)	X ^f				X					X				X				X				X	
Vital Signs ⁱ	X ^{f,i}	X ⁱ	X	X	X	X	X	X	X	X	X	X	X	X		X		X		X		X	
Body Weight	X				X					X				X				X				X	
TB Testing ^j					X					X				X				X				X	
Pregnancy Testing ^{k,q}	X ^f	X	X	X	X	X	X	X	X	X	X	X	X	X	X	X	X	X	X	X	X	X	X
Local Tolerability Assessment	X	X	X	X	X	X	X	X	X	X	X	X	X	X		X		X		X		X	

Activity	Visit 1/Baseline ^a	Visit 2/Week 12	Visit 3/Week 24	Visit 4/Week 36	Visit 5/Week 48	Visit 6/Week 60	Visit 7/Week 72	Visit 8/Week 84	Visit 9/Week 96	Visit 10/Week 108	Visit 11/Week 120	Visit 12/Week 132	Visit 13/Week 144	Visit 14/Week 156	Week 168	Visit 15/Week 180	Week 192	Visit 16/Week 204	Week 216	Visit 17/Week 228	Week 240	EOT Visit ^b	EOO Visit	
Clinical Laboratory Tests (Chemistry, Hematology, Urinalysis) ^l	X ^f	X	X	X	X ¹	X	X	X	X	X ¹	X	X	X	X ¹		X		X ¹		X		X ¹		
Blood Sampling for PK	X ^f				X				X					X				X				X		
Blood Sampling for ADA Assay	X ^f				X				X					X				X				X		
PASI, sPGA	X ^f	X	X	X	X	X	X	X	X	X	X	X	X	X		X		X		X		X		
NAPSI, PPASI, PSSI	X ^f		X		X		X		X		X		X	X		X		X		X		X		
Dermatology Life Quality Index (DLQI) ^m	X ^f		X		X		X		X		X		X	X		X		X		X		X		
Study Drug Administration	X	X	X	X	X	X	X	X	X	X	X	X	X	X	X ^r	X	X ^r	X	X ^r	X	X ^r	X ^r	X ^o	
Study Drug Dispensation for Self-Administration ^p														X		X		X		X				
Training subject on self-administration and product complaints														X										
Monitoring for Hypersensitivity Reactions	X	X	X	X	X	X	X	X	X	X	X	X	X	X		X		X		X		X		

- a. The Baseline visit date will serve as reference for all subsequent visits. A ± 7-day window is permitted around all study visits after Baseline.

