Week 84	589	[548, 631]
Week 96	673	[632, 715]
Week 108	757	[716, 799]
Week 120	841	[800, 883]
Week 132	925	[884, 967]
Week 144	1009	[968, 1051]
Week 156	1093	[1052, 1177]
Week 180	1261	[1178, 1345]
Week 204	1429	[1346, 1513]
Week 228	1597	[1514, 1681]
Week 252	1765	[1682, 1835]

a. If time is collected in vital signs, restrict to records prior to the first dose of RZB in Study M15-997.

Note: Rx Day calculated relative to first dose date of risankizumab.

Table 11. Visit Windows for Analysis of NAPSI, PPASI, PSSI, and DLQI (UST_RZB, FUM_RZB, RZB_Japan Populations)

Window Label	Target Day	Interval
Entry of Study M15-997	1	≤ 1
Week 24	169	[2, 253]
Week 48	337	[254, 421]
Week 72	505	[422, 589]
Week 96	673	[590, 715]
Week 108	757	[716, 799]
Week 120	841	[800, 925]
Week 144	1009	[926, 1051]
Week 156	1093	[1052, 1177]
Week 180	1261	[1178, 1345]
Week 204	1429	[1346, 1513]
Week 228	1597	[1514, 1681]
Week 252	1765	[1682, 1835]

Note: Rx Day calculated relative to first dose date of risankizumab.

Definition of Missing Data Imputation

No global imputation is taking place at the database level. Efficacy related imputations are outlined in Section 10.0. There is no imputation for missing values in the safety analyses.

Rounding of Numeric Results

Rounding will be performed for presentation of results. No rounding will be performed before or during analyses. The ROUND function of SAS will be used to round results.

When dichotomizing continuous variables, associated continuous variables will be rounded to 9 decimal points before applying the cutoff point to determine the response status (for example, percent change from baseline in PASI score will be rounded to 9 decimal places before comparing to 90%).

The mean and median will be rounded for presentation to 1 decimal more than the data entered into the database. The standard deviation will be rounded to 2 decimal places more than the data entered into the database. The minimum and maximum values will be presented as entered into the database.

Probabilities will be rounded to 3 decimal places before assignment of statistical significance and will be presented in rounded format. Probabilities that round to zero or are reported by SAS as zero will be presented as "< 0.001." Probabilities that round to 1 or are reported by SAS as 1 will be presented as "> 0.999."

7.0 Demographics, Baseline Characteristics, Medical History, and Previous/Concomitant Medications

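### SAP Table 11 gives DLQI, NAPSI, PPASI and PSSI a Week 108 window, but none of them is scheduled at Week 108

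*SAP*

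**What the plan says.** - **Assessment schedule.** In Protocol Appendix C, the row for "NAPSI, PPASI, PSSI" and the DLQI row carry the same marks: Baseline, Weeks 24, 48, 72, 96, 120, 144, 156, 180, 204, 228 and EOT (Week 252). Visit 10/Week 108 is blank in both. PASI and sPGA are marked there. On timing, "A ± 7-day window is permitted around all study visits after Baseline".
- **Window rule.** SAP Section 6.0 introduces its tables as "The protocol specified visits and corresponding time windows used in the efficacy analyses", and says "The threshold between adjacent visits is determined by splitting the interval evenly between the visits".
- **The table in question.** SAP Table 11, "Visit Windows for Analysis of NAPSI, PPASI, PSSI, and DLQI (UST_RZB, FUM_RZB, RZB_Japan Populations", lists Week 96 [590, 715], Week 108 (target Day 757) [716, 799] and Week 120 [800, 925].
- **Comparable tables.** Table 7, and the Switch at OLE part of Table 9, cover the same instruments on the same extension schedule. Neither has a Week 108 row. Both give Week 96 as [590, 757] and Week 120 as [758, 925].
- **Reporting.** SAP Section 10.3 says "The following additional efficacy variables will be summarized at all visits for each population". SAP Section 10.1 says "LOCF will be used as the primary imputation method and OC will be used as sensitivity analysis". Protocol Section 5.3.3.2 is narrower: it limits summaries of these variables to visits at which they are evaluated.

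**The concern.** An analysis window should correspond to a planned measurement. Table 11 creates a time point for which the protocol collects nothing, and the reporting rules then require results there.

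In the LOCF analysis, DLQI 0, DLQI 0/1, the 5-point DLQI reduction and the changes in DLQI, NAPSI, PPASI and PSSI would appear at Week 108 as a further point of sustained response, although nobody was due to be assessed. In the observed-case analysis the same row would rest on a few subjects with displaced visits.

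The row also harms its neighbours. A Week 96 assessment done late, on Days 716 to 757, is moved out of Week 96. The subject then drops out of Week 96 in the observed-case analysis and is represented by an older value, normally Week 72, under LOCF.

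**Working it through.** **Inputs.** Target day = 7 × week + 1, the convention in all the SAP window tables. Assessment weeks and the ±7-day allowance come from Appendix C, and the splitting rule from SAP Section 6.0.

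**1. Reproduce Table 11 as printed.** Targets are Week 96 = 673, Week 108 = 757 and Week 120 = 841.

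- (673 + 757)/2 = 715, so Week 96 ends on Day 715.
- (757 + 841)/2 = 799, so Week 108 is [716, 799] and Week 120 starts on Day 800.

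The other intervals in Table 11 also reproduce, taking the final upper bound of 1835 as given. The printed limits of 715 and 799 therefore arise only if Week 108 is treated as a scheduled assessment.

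**2. Apply the same rule to the actual schedule.** Without Week 108, the neighbours are Days 673 and 841, and (673 + 841)/2 = 757.

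| Window | Table 11 | Actual schedule | Tables 7 and 9 (OLE) |
|---|---|---|---|
| Week 96 | [590, 715] | [590, 757] | [590, 757] |
| Week 108 | [716, 799] | none | none |
| Week 120 | [800, 925] | [758, 925] | [758, 925] |

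All other Table 11 rows are unchanged.

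**3. Which scheduled values can reach [716, 799]?**

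- Week 96 ± 7 days: Days 666 to 680. The latest is short of 716, and entry needs a delay of at least 716 − 673 = 43 days.
- Week 120 ± 7 days: Days 834 to 848. The earliest is beyond 799, and entry needs an assessment at least 841 − 799 = 42 days early.

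Scheduled values in the window: none.

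**4. Days taken from the real windows.** The span is 799 − 716 + 1 = 84 days: 42 from Week 96 (716 to 757) and 42 from Week 120 (758 to 799). For example, a Week 96 assessment on Day 720 (47 days late) goes to Week 108 under Table 11 but to Week 96 under the corrected windows.

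**5. Is Table 11 alone?** The tables on a first-dose clock can be aligned by where extension Week 156 falls: Week 208 in Table 2, Week 192S in Table 4 and Week 184S in the Week 16 switch part of Table 9. The offsets are 52, 36 and 28 weeks, so extension Week 108 would be Week 160, Week 144S and Week 136S. None of these tables has such a row. Table 11 is the only one that does, and its interval matches the Week 108 row of Table 10, where it is right for PASI and sPGA. A carry-over from Table 10 is a plausible origin.

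**The case against.** The strongest objections concern consequence and certainty, since the row and the blank schedule cells are both plain.

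- **The protocol may override.** Section 5.3.3.2 restricts summaries to visits where the variable is evaluated, and an assessment never planned is arguably not missing data for LOCF to fill. That reading is possible. But Table 11 names Week 108 as an analysis visit and SAP Section 10.3 asks for all visits, so a programmer following the SAP would produce the row. The conflict with the protocol is a further reason to remove it.
- **The clock.** The note under Table 11 counts days from the first risankizumab dose, and RZB_Japan may include subjects first dosed in a preceding study. With an assumed lead-in of 36 weeks, extension Week 72 falls on Day 505 + 252 = 757; with 40 weeks, on Day 505 + 280 = 785. Both are inside the window. Lead-ins of 24, 28, 44 or 52 weeks put no target day there. The ambiguity is real, but the first row is labelled as entry to M15-997, the Table 10 footnote refers to the first dose in M15-997, and RZB_Japan is defined on extension visits. All three point to the extension clock.
- **The splitting rule.** When a midpoint falls on a day, the rule's text and its own example disagree by one day. The printed tables follow the example and put the midpoint day in the earlier window, as done here. Table 7 also has an error of its own: its Week 156R target, Day 1093, lies inside the Week 144R window. Table 9 is the better model.
- **Size.** Displacements of six weeks should be uncommon, and the documents give no frequency. Values after study drug discontinuation are excluded, which removes many early EOT assessments. The observed-case counts would reveal a near-empty row. These points stand and limit the importance of the error, but none of them supports keeping the row.

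**Conclusion.** The concern holds. Table 11 contains a Week 108 window with no scheduled assessment behind it, contrary to Appendix C, to the SAP's own basis for its windows and to the comparable tables.

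With on-time visits, essentially the whole LOCF row is carried forward, from Week 96 for most subjects and from an earlier visit for those who missed Week 96. The observed-case row contains only off-schedule assessments. The two real windows lose 42 days each.

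This affects all DLQI, NAPSI, PPASI and PSSI summaries at Weeks 96, 108 and 120 in three populations. At Weeks 96 and 120 it matters only for subjects with badly displaced assessments. The variables are additional rather than key, the analysis is descriptive, and safety, PASI and sPGA are unaffected. It should be corrected, but it does not threaten the study's main conclusions.

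The verdict assumes that Rx Day in Table 11 runs from the first dose in M15-997 and that UST_RZB and FUM_RZB subjects start risankizumab at extension entry.

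**What to change.** In SAP Table 11, delete the Week 108 row, set Week 96 to [590, 757] and set Week 120 to [758, 925]. These match the Switch at OLE part of Table 9. Leave Week 108 in Table 10. In the same edit, state in the notes to Tables 10 and 11 that Rx Day is counted from the first dose in M15-997, if that is what is meant, and align the wording of SAP Section 10.3 with Protocol Section 5.3.3.2.

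The cost is one deleted row, two changed intervals, a clarified note and an update to the windowing program. No scheduled data are lost: where an off-schedule value shares a window with an on-time one, the SAP's closest-to-target rule keeps the on-time value. If the second interim analysis has already used the printed windows for UST_RZB and FUM_RZB, interim and final tables may differ slightly at Weeks 96 and 120, and the change should be recorded in SAP Section 14. RZB_Japan is analysed only at the end of the study and has no such issue.
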